5. PLANNED ANALYSES

The following analyses will be performed for this study:

- Analyses to be used for dose escalation decisions (Part A)
- Analyses for DSMC meetings (Part A and B)
- Futility monitoring (Part B)
- Final analysis for the Main study period
- Final analysis for the Extended study period

5.1. DOSE ESCALATION DECISIONS (PART A)

After each 3 or 6 evaluable patients, the DLTs in cycle 1 will be assessed and a decision on the next dose will be made following the classic 3+3 design (refer to Section 4.1.2).

To support this, patient profiles, based on raw data, will be produced including the following information:

- DLTs
- Patient evaluability
- Demographic characteristics
- Tumour type and cancer history
- Medical history
- Previous anti-cancer therapies
- Debio 1143 exposure & modifications
- Nivolumab exposure & modifications
- AEs, serious adverse events (SAEs), and adverse events of special interest (AESIs)
- Prior and concomitant medications
- Lab parameters
- Screening laboratory assessments
- Endocrinology
- All efficacy data including target, non-target and new lesions. Also, response as assessed by RECIST/GCIG will be presented
- Vital signs
- ECOG performance status

Document: T:\sas\Debiopharm\Debio_1143\CZA60507\Biostatistics\Documentation\SAP\SAP Text\IV5

Author: [REDACTED] Version Number: 5.0
Version Date: 19APR2022

Template No.: CS_TP_BS016 Revision 5
Effective Date: 01Apr2018

Reference: CS_WI_BS005

- Treatment/study withdrawal information
- Deaths

In addition, a table summarising the subject disposition will be provided with the patient profiles.

The templates for the patient profiles are provided in a separate document: Debio 1143-106 Patient Profile Shells FINAL.

5.2. DATA SAFETY / EFFICACY MONITORING COMMITTEE (DSMC)

A DSMC will overview study conduct during both parts A and B. It will be composed of at least all actively involved investigators (or their designee), the Sponsor Medical Director and the Contract Research Organization (CRO) medical monitor as voting members, and will meet regularly to overview the clinical safety of the patients, laboratory data and the conduct of the study. Ad hoc members may be invited as needed. The full details regarding the composition of the DSMC and the timing of analyses will be included in the DSMC charter.

For part A, only the patient profiles as described in section 5.1 will be produced for DSMCs. For part B, TLFs will be produced once there are at least 4 patients enrolled in each cohort or at least 15 patients overall, whichever occurs first. Until then, only the patient profiles as described in section 5.1 will be produced. The TLFs to be produced for DSMC analyses will be indicated in the Debio 1143-106 TLF Shells FINAL document and the DSMC charter.

5.3. FUTILITY MONITORING ANALYSES

There will be two futility monitoring analyses in each cohort. The cut-off for futility analyses is defined as the time when the last ongoing patient from the first 8/11 evaluable patients has at least 2 post-baseline tumor assessments or prematurely discontinued.

No formal interim analysis will be performed during the futility monitoring. Only the number of evaluable patients with, at least, unconfirmed responses as per RECIST v1.1 and/or GCIG criteria (if applicable) will be checked vs. the futility boundaries in each cohort independently.

Bayesian posterior probability of the unconfirmed objective rate will be used for the early stopping rules for futility.

A general confirmed response rate of 15% is considered as promising, justifying further development. This corresponds to approximately 17% unconfirmed response rate. On the other hand, 5% is considered to be the general futility response rate (unconfirmed).

Document: T:\sas\Debiopharm\Debio_1143\CZA60507\Biostatistics\Documentation\SAP\SAP Text\V5

Author: XXXXXXXXXX Version Number: 5.0
Version Date: 19APR2022

Template No.: CS_TP_BS016 Revision 5
Effective Date: 01Apr2018

Reference: CS_WI_BS005

Assuming a probability confidence threshold for futility stopping of 20%, and a maximum sample size of 15 evaluable patients by cohort, the futility stopping boundaries are defined for each cohort as follows:

- 0 unconfirmed response out of 8 evaluable patients for the first futility monitoring analysis and
- ≤ 1 unconfirmed response out of 11 evaluable patients for the second futility monitoring analysis

Consequently, if no unconfirmed objective response is documented as per RECIST v1.1 and/or GCIG criteria (if applicable) after the 8th evaluable patient is assessed, futility will then be concluded and the recruitment will be stopped in the corresponding cohort. In case at least one unconfirmed response is documented in the first 8 evaluable patients, recruitment shall continue up to 11 evaluable patients and a second futility monitoring analysis will be conducted. If at least two unconfirmed responses are documented in the first 11 evaluable patients, the recruitment will continue up to 15 evaluable patients; otherwise the recruitment will be stopped. The early stopping for futility is binding.

The Bayesian posterior probability will be used to preliminary assess the primary efficacy endpoint: the confirmed ORR as per RECIST v1.1 and/or GCIG criteria, if applicable. The unconfirmed ORR will be used for the early futility stopping rules.

The main metrics of the Bayesian efficacy monitoring via posterior probability are the following:

- Denote θ as the response rate. The prior distribution of θ is: $\theta \sim \text{Beta}(a_0, b_0)$
- Let R be the number of responses in n observations, $R \sim \text{Binomial}(\theta, n)$.
- The posterior distribution of θ given observed r responses and $n-r$ no responses is:

$$\theta | r, n \sim \text{Beta}(a_0+r, b_0+n-r).$$

For futility monitoring, the following decision rules are introduced:

1. Early stopping for futility: let θ_{fut} be the reference response rate for futility monitoring and P_{fut} be the probability confidence threshold for futility. The trial should be stopped early and the treatment is declared inefficacious if

$$\text{Prob}(\theta \leq \theta_{fut} | r, n) > P_{fut}.$$

2. Criterion for declaring efficacy: let $\theta_{eff, final}$ be the reference response rate for declaring efficacy at the final stage, and $P_{eff, final}$ be the probability confidence threshold for final efficacy.

The treatment is declared efficacious at the end of the trial if

$$\text{Prob}(\theta > \theta_{eff, final} | r, n) \geq P_{eff, final}.$$

In this trial, the metrics are the following:

Metric	Value
Reference response rate for futility monitoring (θ_{fut})	0.05

Document: T:\sas\Debiopharm\Debio_1143\CZA60507\Biostatistics\Documentation\SAP\SAP Text\V5

Author: [REDACTED] Version Number: 5.0
Version Date: 19APR2022

Template No.: CS_TP_BS016 Revision 5
Effective Date: 01Apr2018

Reference: CS_WI_BS005

Probability confidence threshold for futility stopping (P_{fut})	0.2
Reference response rate for efficacy ($\theta_{eff,final}$)	0.15 for confirmed ORR and 0.17 for unconfirmed ORR
Probability confidence threshold for declaring efficacy ($P_{eff,final}$)	0.8
Prior distribution for theta: Beta (α_0, b_0)	(0.5, 0.5)
Maximum number of patients per cohort	15

The futility boundaries are described in the table below:

# Patients (inclusive)	# Responses (inclusive) to be considered as non-futile
8, 9 & 10	≥ 1
11, 12, 13 & 14	≥ 2

The TLFs to be produced for the futility monitoring analyses (for all evaluable and non-evaluable patients) will be indicated in the Debio 1143-106 TLF Shells FINAL document and they will cover the following:

- Subject disposition
- Exclusion from analysis sets
- Demographics
- Baseline disease characteristics
- Study drug exposure (Debio 1143 and Nivolumab)
- Unconfirmed best overall response and unconfirmed objective response rate
- Swimmers plot including previous anticancer therapies

5.4. FINAL ANALYSIS FOR THE MAIN STUDY PERIOD

All final, planned analyses identified in this SAP for the Main study period will be performed by IQVIA Biostatistics following Sponsor authorization of this SAP, Sponsor authorization of analysis sets, and Database Freeze .

The final analysis for the Main study period will include all study endpoints and will be performed within one year of the End of the Main study period i.e., 18 months after the last patient in (LPI) or 60 days after the last patient last visit (LPLV), whichever occurs first . The main study results will be presented separately for both study parts. Only data collected during the Main study period will be included in the final analysis of the Main study period.

Document: T:\sas\Debiopharm\Debio_1143\CZA60507\Biostatistics\Documentation\SAP\SAP Text\5
 Author: ██████████ Version Number: 5.0
 Version Date: 19APR2022

Template No.: CS_TP_BS016 Revision 5 Reference: CS_WI_BS005
 Effective Date: 01Apr2018

Copyright © 2009, 2010, 2012, 2016, 2018 IQVIA. All rights reserved. The contents of this document are confidential and proprietary to IQVIA Holdings Inc. and its subsidiaries. Unauthorized use, disclosure or reproduction is strictly prohibited.

5.5. FINAL ANALYSIS FOR THE EXTENDED STUDY PERIOD

Data collected after the Main study period for patients entering the Extended study period will be analysed using descriptive statistics and included in an addendum to the Final CSR. If only few patients or few visits are collected, data will be reported as individual listings.

6. ANALYSIS SETS

Agreement and authorization of subjects included/excluded from each analysis set will be conducted prior to the final analysis of the Main study period.

6.1. SCREENED ANALYSIS SET

The screened (SCR) analysis set contains of all subjects who signed the informed consent form.

6.2. RP2D ANALYSIS SET (PART A ONLY)

Patients will be considered as not evaluable for DLTs and excluded from the RP2D analysis set, if they did not receive at least 70% of Debio 1143 (i.e. a maximum of 6 missed Debio 1143 doses is allowed) and at least one nivolumab dose as planned in cycle 1 for any reason other than DLT.

Patients not evaluable for DLT will be replaced if there are less than 3 evaluable patients by cohort.

If a treatment modification during the DLT period leads to a potentially non-evaluable patient, the final decision regarding the patient's evaluability will be taken only at the end of his/her DLT period. If the patient experiences a DLT, he/she will be considered as evaluable regardless of his/her exposure.

RP2D is not applicable for part B because TLFs will not be produced based on this analysis set for part B.

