

STUDY POPULATION
	
Patients with selected advanced/unresectable or metastatic solid tumors, for whom standard therapy has failed, including progression to prior treatments with anti PD-1/PD-L1 given as single agent or in combination with standard/approved chemotherapy, TKIs or other targeted agents, RT, hormonal therapy or any other non-CPI mAbs, but excluding other antibody or drug specifically targeting T-cell co-stimulation or immune checkpoints pathways (i.e., CTLA-4). Any other potential CPI combinations previously administered to the candidate should be discussed and agreed by the Sponsor before patient inclusion.
 
The same indications will be eligible in both study Part A and B. In Part B, separate cohorts are defined as follows.
 
Part A:
 
 
• Between 3 and 12 patients evaluable for DLT planned.
 
• Patients will be evaluable for DLT if they received at least 70% of Debio 1143 and one planned nivolumab dose during Cycle 1 and were evaluated for DLT or if the patient discontinued treatment earlier due to any toxicity that could be considered a DLT.
 
• Non-evaluable patients will be replaced, as appropriate.
 
 
Part B:
 
Cohort 1: SCLC (including extrapulmonary small-cell carcinomas or large cell neuroendocrine lung carcinoma, as per WHO Classification of Lung Tumors of 2015)
 
Cohort 2: SCCHN (nasopharyngeal carcinomas are excluded)
 
Cohort 3: GI cancers (including esophageal, gastric, colorectal or pancreatobiliary) with known MSI-H/MMRd or other DDRs abnormalities, including HRD.
 
Cohort 4: platinum-resistant EOC, endometrial cancer, PPC or cervical cancer, with known MSI-H/MMRd, hereditary/somatic mutations of the BRCA1 and BRCA2 genes or other DNA DDR abnormalities (incl. HRD).
 
 
• Between 32 (if all cohorts are futile) and 60 evaluable patients (if none of the 4 cohorts is futile).
 
• Patients will be evaluable for efficacy if the two conditions below are met:             
 
a. Measurable disease at baseline as per RECIST v1.1 or GCIg criteria (Cohort 4),
 
b. At least one efficacy assessment done, either computed tomography (CT) or magnetic resonance imaging (MRI) for RECIST evaluable patients; or CA-125 dosage performed after baseline, if applicable or treatment discontinuation occurred before the efficacy assessment is done due to treatment failure, defined as any of the following: death, unacceptable toxicity, clinical deterioration and/or symptoms worsening.
 
 
 
• Non-evaluable patients will be replaced.
 

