## 5.2. DLT period and definition of DLTs

The DLT period is defined as Cycle 1\*.

DLT is defined as any of the following treatment-emergent adverse events (TEAEs) which are possibly, probably or definitely related to the combination treatment and occurring in Cycle 1 (1 cycle=4 weeks):

- Any Grade 4 or 5 hematologic toxicity, clinical or laboratory non-hematologic toxicity
- Febrile neutropenia any grade, Grade 3 thrombocytopenia if associated with bleeding or requiring platelet transfusion
- Grade 2 or higher cardiac or neurologic toxicities, pneumonitis that does not resolve within 3 days after starting steroids at adequate doses or that was recurrent upon steroid tapering or withdrawal, myasthenia gravis, myositis, polymyositis, Guillain-Barre syndrome (excluding peripheral purely-sensory neuropathies)
- Grade 2 or higher alanine transaminase (ALT)/ aspartate transaminase (AST) increase with a concurrent increase of total bilirubin  $\geq 2$  x upper limit of normal (ULN) and concurrent with alkaline phosphatase (ALP)  $\leq 2$  x ULN (Hy's law), in the absence of objective causes of biliary obstruction due to obvious disease-related causes
- Any other Grade 3 non-hematologic, treatment-related clinical toxicity lasting 3 or more days despite optimal supportive care, or requiring admission for appropriate medical management; hypersensitivity and/or infusion-related reactions are excluded if not reoccurring after appropriate pre-medication and/or prolonging infusion time
- Grade 3 non-hematologic laboratory value (excluding lipase, amylase and/or autoimmune endocrinopathies manageable by replacement therapies) if:
  - a. Symptomatic and
  - b. Medical intervention was promptly required to treat the patient, or
  - c. The abnormality led to hospitalization or
  - d. The abnormality did not resolve to at least Grade 1 within 2 weeks (including the steroid tapering period) despite adequate medical intervention/treatment
- A delay of >2 weeks due to drug-related toxicity in initiating Cycle 2
- Unable to complete at least 70% of the scheduled treatment, i.e. more than six Debio 1143 skipped doses in Cycle 1 due to treatment-related toxicity
- Required dose reduction in Cycle 1 or on Cycle 2 Day 1 or requirement for treatment withdrawal due to treatment-related toxicity (even if not meeting other DLT criteria)

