### **6.3. Patient replacement**

#### Part A

Patients will be evaluable for DLT, if they received at least 70% of Debio 1143 (i.e., a maximum of 6 missed Debio 1143 doses) and at least one nivolumab dose as planned in Cycle 1 and were evaluated for DLT or if the patient discontinued treatment early due to any toxicity that could be considered a DLT.

Non-evaluable patients will be replaced, as appropriate (see [section 11.5.1](#)).

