### **11.5. Selection of patients for statistical analysis**

#### **11.5.1. RP2D population (part A only)**

Patients will be considered as not evaluable for DLTs and excluded from the RP2D population, if they did not receive at least 70% of Debio 1143 (i.e., a maximum of 6 missed Debio 1143 doses) and at least one nivolumab dose as planned in Cycle 1 for any reason other than DLT.

Patients not evaluable for DLT will be replaced if there are less than 3 evaluable patients by cohort.

If a treatment modification during the DLT period leads to a potentially non-evaluable patient, the final decision regarding the patient's evaluability will be taken only at the end of his/her DLT period. If the patient experiences a DLT, he/she will be considered as evaluable regardless his/her exposure.

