18. SAFETY OUTCOMES

All outputs for safety outcomes will be based on the SAF analysis set except the DLT summaries and listing which will be on the RP2D analysis set.

Document: T:\sas\Debiopharm\Debio_1143\CZA60507\Biostatistics\Documentation\SAP\SAP Text\V5

Author: XXXXXXXXXX Version Number: 5.0
Version Date: 19APR2022

Template No.: CS_TP_BS016 Revision 5
Effective Date: 01Apr2018

Reference: CS_WI_BS005

Copyright © 2009, 2010, 2012, 2016, 2018 IQVIA. All rights reserved. The contents of this document are confidential and proprietary to IQVIA Holdings Inc. and its subsidiaries. Unauthorized use, disclosure or reproduction is strictly prohibited.

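### The protocol defines DLT evaluability in two ways, and the version repeated in SAP 6.2 keeps DLT-free patients whose Cycle 1 was only partly observed

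*SAP*

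**What the plan says.** Two definitions of DLT evaluability stand side by side.

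- **Protocol synopsis (study population, Part A) and protocol 6.3.** A patient needs at least 70% of the Debio 1143 doses and at least one nivolumab dose in Cycle 1. Protocol 6.3 adds "and were evaluated for DLT or if the patient discontinued treatment early due to any toxicity that could be considered a DLT". The synopsis has the same second limb: "and were evaluated for DLT or if the patient discontinued treatment earlier due to any toxicity".
- **Protocol 11.5.1 and SAP 6.2.** Protocol 11.5.1 has patients "excluded from the RP2D population, if they did not receive at least 70% of Debio 1143" and one nivolumab dose, for any reason other than DLT. SAP 6.2 repeats this almost unchanged: patients are "excluded from the RP2D analysis set, if they did not receive at least 70% of Debio 1143", with the same nivolumab condition. Neither requires that a patient without a DLT was assessed for one.

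SAP 6.2 has two further rules. One protects patients with a DLT: "If the patient experiences a DLT, he/she will be considered as evaluable regardless of his/her exposure". The other defers the evaluability decision to the end of the DLT period, but only where a treatment modification has made the patient potentially non-evaluable. Replacement applies only to patients classed as not evaluable.

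SAP 18 puts safety outputs on the safety set, "except the DLT summaries and listing which will be on the RP2D analysis set". SAP 5.1 bases escalation decisions on groups of 3 or 6 evaluable patients, and 6.2 is the SAP's only definition of DLT evaluability. SAP 4.3, which lists changes from the protocol, is silent on the point.

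**The concern.** The Part A primary endpoint is the RP2D, defined by DLTs in fewer than one third of evaluable patients at that dose, with 3 to 6 patients per level. Who belongs in the denominator therefore matters at the level of a single patient. An exposure threshold does not establish that the DLT window was watched: it can be met well before Day 28. Some DLT criteria also look past Day 28. Protocol 5.2 counts a delay of more than two weeks in starting Cycle 2, and "Required dose reduction in Cycle 1 or on Cycle 2 Day 1". Neither Cycle 2 element can be read in a patient who has left the study. If such a patient is kept as DLT-free, the error has one direction, because unobserved time can conceal a DLT but cannot create one. The classification also bears on the protocol's requirement of at least six evaluable patients at the RP2D before Part B.

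**Working it through.** **Inputs.** Dosing on Days 1–10 and 15–24 of a 28-day cycle, nivolumab on Days 1 and 15, DLT period of Cycle 1 (protocol 5.1.1, SAP 4.1.1). Threshold of 70%, given as at most 6 missed doses (SAP 6.2). Part A on-site days in Cycle 1: 1, 3, 8, 15, 17 and 22 (protocol Table 8-6).

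**Step 1: the plan's own figure.** 10 + 10 = 20 doses; 0.70 × 20 = 14; 20 − 14 = 6 missed. The SAP's figure is reproduced.

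**Step 2: the earliest exit that still passes, with every dose taken until then.**

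- After Day 17: 13/20 = 65%, fails.
- After Day 18: 14/20 = 70%, passes; both infusions given; 28 − 18 = 10 days (36%) unobserved.
- After the Day 22 visit: 18/20 = 90%, passes; 28 − 22 = 6 days (21%) unobserved.

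Day 18 is not a scheduled visit, so that dose would have to be documented by diary or an unscheduled contact. Day 22 is the more natural last contact.

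**Step 3: classification.** Under protocol 6.3, a patient who was not evaluated for DLT is non-evaluable and replaced. Under protocol 11.5.1 and SAP 6.2, the same patient is evaluable without DLT. No treatment modification has made the patient potentially non-evaluable, so the deferral rule does not apply.

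**Step 4: illustration of size.** The documents give neither a DLT rate nor its timing. Assume a true Cycle 1 rate p = 1/3 and constant hazard. The chance of no DLT by day d is s = (1 − p)^(d/28).

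- Day 18: s = (2/3)^(18/28) = 0.7705, so a DLT is seen with probability 22.9% instead of 33.3%.
- Day 22: s = (2/3)^(22/28) = 0.7272.

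With five fully observed patients and one other, P(≤1 DLT in 6) = (2/3)^5 + s × 5 × (1/3) × (2/3)^4 = 0.1317 + 0.3292 s.

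- All six observed (s = 2/3): 0.1317 + 0.2195 = 35.1%.
- One lost after Day 18: 0.1317 + 0.2537 = 38.5%.
- One lost after Day 22: 0.1317 + 0.2394 = 37.1%.

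With two of six lost after Day 18 the figure is 42.2%. The expected reported DLT proportion with one patient lost after Day 18 is (5 × 0.3333 + 0.2295)/6 = 31.6%, against 33.3%.

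**Step 5: range over the assumed rate, one of six lost after Day 18.** At 20%: 65.5% to 68.3%. At 40%: 23.3% to 26.4%. At 50%: 10.9% to 13.1%. The criteria tied to Cycle 2 are not included in any of these figures.

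**The case against.** The strongest reply is that few patients fall into the gap. Stopping treatment is not the same as going unobserved. Protocol 8.3.2.1 sets an end-of-treatment visit 30 days (± 5) after the last Debio 1143 dose, which for a last dose on Day 18 is about Day 48. Protocol 8.2.2.1 records adverse events up to 5 months after the last nivolumab infusion, absent new therapy or end-of-life care. A reader might infer that a patient who stops for progression on Day 19 is unobserved; the documents do not support that. Withdrawal for treatment-related toxicity is itself a DLT under protocol 5.2, so those patients are evaluable under every definition. Both arguments stand. They narrow the point to consent withdrawal, loss to follow-up, and early start of new therapy or end-of-life care.

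A reader might also infer that the SAP removed a protocol condition. It did not: it carries over protocol 11.5.1, so the conflict begins inside the protocol.

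Finally, a reader might infer that the RP2D was chosen on a biased count. The documents do not show that. Dose decisions were taken at DSMC meetings on patient profiles that show evaluability, exposure, adverse events and withdrawal, and the DSMC could have applied protocol 6.3. The RP2D also draws on overall safety, PK and compliance. SAP version 5.0 already reports Part B futility, so its wording cannot steer that decision now. What it does govern is the reported DLT denominator, because SAP 6 has set membership agreed before the final Main study period analysis.

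**Conclusion.** The contradiction is real and sits within the protocol: the synopsis and 6.3 on one side, 11.5.1 and SAP 6.2 on the other. Followed as written, SAP 6.2 keeps an incompletely assessed, DLT-free patient in the RP2D set, and the reported DLT proportion is then biased downward. Whether the dose decision was also biased depends on which definition the DSMC used, which the documents do not say. Nor do they say whether any such patient occurred.

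The size is modest per patient: about 3 percentage points on the chance of at most one DLT in six for an exit after Day 18, and 2 points for an exit after Day 22. Both rest on an assumed rate of 1/3, constant hazard and one affected patient. The reason to act is that the denominators are tiny, the direction is known, and the correction is cheap.

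**What to change.** Reconcile the passages. In SAP 6.2 and protocol 11.5.1, add the protocol 6.3 condition that the patient was evaluated for DLT, and state it as DLT assessment completed through the end of the DLT period. Protocol 6.3 does not itself say how far the evaluation must run, so this is a clarification and should be recorded as one, with an entry in SAP 4.3. Keep both existing alternatives: a patient with a DLT is evaluable whatever the exposure, and so is a patient who stopped early for a toxicity that could be considered a DLT.

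Before the analysis sets are authorised, list any Part A patient who met the exposure rule without a complete Cycle 1 DLT assessment, and report the DLT proportion accordingly. If there are none, say so.

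The cost is one sentence in each document and one listing check. The downside is an occasional replacement patient or, where replacement is no longer possible, a smaller evaluable denominator, which could fall below the six required at the RP2D.
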